6.2. Adjustments for Covariates

Additional exploratory analyses may be performed on efficacy measures to adjust for factors that may affect survival or disease progression. See section [6.17](#) on the covariates that will be considered in the survival models.

6.3. Handling of Dropouts or Missing Data

The number of patients that discontinued early from treatment and the reason for discontinuation will be summarized for each treatment arm. See Sections [6.5](#) and [6.6](#) on the method for handling these patients in the analyses.

The primary method for handling missing time-to-event data will be censoring. See details on censoring for each time-to-event endpoints in [Section 6.10](#).

6.4. Multiple Comparisons/Multiplicity

No adjustment for multiplicity is planned for this study. The primary analysis will compare the OS distributions for only LY2157299 plus lomustine and placebo plus lomustine. Comparisons between other treatment arms will secondary or exploratory in nature.

6.5. Use of an “Efficacy Subset” of Patients

The efficacy analyses on time-to-event endpoints will be conducted on all patients who received at least 1 dose of any study drug. Patients that discontinued after randomization and did not receive study treatment for reasons other than not meeting entry criteria will be followed for survival till death occurs. Since the effect of the study drug is not realized in these patients, the time-to-event analyses will not include these patients.

Patients that did not meet entry criteria after receiving study treatment (for example, protocol violators) will be included in the main efficacy and safety analyses. However, a subanalysis will be conducted by excluding these patients who should have been otherwise discontinued to determine their influence on the final study results.

6.6. Patient Disposition

A detailed description of patient disposition will be provided. It will include a summary of the number and percentage of patients entered into the study, enrolled in the study, and treated as well as number and percentage of patients discontinuing (overall and by reason for discontinuation) from both study treatment and study itself in each arm. All entered patients will be accounted for in this summary of disposition. Screen failures and patients who died or discontinued before treatment begins will be specified.

A listing of primary reasons for both study treatment and study discontinuation will also be provided according to each treatment arm. A listing of patients who discontinued due to AE or death from treatment and study itself will also be provided with additional information on cause of death and the AE associated with discontinuation.

6.7. Patient Characteristics

Patient demographics and physical characteristics including age at consent, sex, race, height, screening weight, and body surface area (BSA) will be listed and summarized using descriptive statistics for all enrolled patients in each arm. Consumption habits of tobacco, alcohol and caffeine/xanthine use will also be included as appropriate.

Special instructions regarding presentation of race: patient may select more than one of the values for Race in the case report form (CRF). Derive Race to 'Multiple' if more than one race is selected. Otherwise, race equals the single race selected. For example, if a patient selects both 'White' and 'Asian' then RACE = 'Multiple'. However, if a patient select only 'Asian' then RACE = 'Asian'.

Baseline disease characteristics will be summarized, by presenting frequency counts and percentages, for pathological diagnosis (histological or cytological), ECOG PS, GB subtypes (primary or secondary) and disease grade.

Prior disease-related regimens will also be listed detailing individual therapies within each regimen (Section 6.9) and summarized by the number of prior regimens.

A patient listing of historical illnesses (using preferred term from the most current version of the Medical Dictionary for Regulatory Activities [MedDRA] and reported term captured in CRF) will also be provided.

Other patient characteristics will be summarized as deemed appropriate.

6.8. Treatment Compliance

The number of dose omissions, reductions, delays, number of cycles received, and dose intensity will be summarized for all treated patients per treatment arm. Summarized data will be provided for the treatment period.

Treatment compliance with LY2157299 or placebo within a cycle means that the patient has taken their allocated LY2157299 or placebo treatment as prescribed for a minimum of 10 days and a maximum of 14 days per 28-day cycle and at least cc1% of the allocated LY2157299 prescribed dose has to be administered within each cycle. Exception is given to patients that discontinued early due to death or other reasons prior to completing a minimum of 10 dosing days in a cycle. These patients would be deemed compliant if at least cc1% of LY2157299 prescribed dose is administered up to the time of discontinuation. This is distinct from dose intensity which calculates the amount of drug taken per cycle compared to the dose the patient was initially assigned at the start of the study and is defined in [Section 6.13.1](#).

Treatment compliance within a cycle means that the patient has taken their allocated treatments as prescribed for that cycle. This information for LY2157299 and placebo will be collected on CRF through both tablet counts (for 50 mg and 10 mg tablets strength) and by the site querying the patient at the end of each cycle for each patient. The level of compliance in percent for a cycle will be calculated as follows:

Compliance in percent = $100\% \times [10 \times (\text{total tablets dispensed} - \text{total tablets returned}) + 50 \times (\text{total tablets dispensed} - \text{total tablets returned})] / (10 \times \text{total tablets dispensed} + 50 \times \text{total tablets dispensed})$

The level compliance will be summarized using descriptive statistics (mean, standard deviation, median, minimum and maximum) by cycle and treatment arm. Overall compliance will be averaged across cycles.

In addition, the number of tablets dispensed and returned will be listed with the level of compliance in each cycle for individual patient.

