9.8. Treatment Compliance

Patient compliance will be assessed by direct questions and count of returned tablets. Deviations from the prescribed dosage regimen should be recorded in the comments section of the eCRF.

LY2157299 and lomustine will be administered orally. Lomustine should be administered under the direction of study personnel. The site, following institutional guidelines, may allow the patient to take the scheduled lomustine dose at home.

Patients who are significantly noncompliant will be discontinued from the study after discussion between Lilly and the investigator. Significant noncompliance includes, but is not limited to the following:

- Compliance of LY2157299 will be determined by the use of at least **80**% of the prescribed/intended amount of drug per cycle (see details in Section 9.1).
- Patient refuses to inform about efficacy and survival measures.
- Patient misses several visits leading to dose delay and/or missed safety assessments.

10. Efficacy, Health Outcome Measures, Safety Evaluations, Sample Collection and Testing, and Appropriateness of Measurements

Study procedures related to efficacy, safety, sample collection, and testing assessments and their timing are described in the sections below and shown in the Study Schedule ([Attachment 1](#)).

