12.2.5. Treatment Compliance

The number of dose omissions, reductions, delays, number of cycles received, and dose intensity will be summarized for all treated patients per treatment arm. Summarized data will be provided for the treatment period.

Treatment compliance within a cycle means that the patient has taken their allocated treatments as prescribed for that cycle (see Section [9.1](#)). (This is distinct from dose intensity which

calculates the amount of drug taken per cycle compared to the dose the patient was initially assigned at the start of the study and is defined in Section 12.2.10).

Treatment compliance information for LY2157299 and placebo will be collected through both pill counts and by the site querying the patient at the end of each cycle for each patient. The number of tablets taken relative to the number expected to be taken will be summarized by cycle and treatment arm.

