6.15. Protocol Violations

Protocol violations will be identified based on information recorded on the investigator log and through statistical programming of the data. A list of data dependent protocol violations in general and specific to this study is as follows:

General:

- Not meeting protocol inclusion/exclusion criteria [2], [3], [5] to [9], [11], [13] to [17]
- If patient with “entry criteria not met” is marked at screening (visit 0) but patient moves on to cycle 1
- Use of prohibited concomitant therapy (See Protocol Section 9.7):
 - Chemotherapy;
 - Radiation therapy;
 - Immunotherapy;
 - Cancer-related hormonal therapy;
 - Surgery for cancer;
 - Experimental/investigational medication;

- Routine use of granulocyte colony-stimulating factors. They may be used for patients who have ANC $\leq 0.5 \times 10^9/L$, neutropenic fever, or documented infections at investigator's discretion, but cannot be used during Visit 0 to meet hematological inclusion criteria and must be discontinued at least 24 hours prior to the start of therapy.
- Any disease progression requiring other forms of specific anti-tumor therapy will be cause for early discontinuation from the study.
- Treatment compliance with LY2157299 is less than **CCI**% of the prescribed/intended amount of drug per cycle
- Incorrect dose administered (e.g., more than intended)
- Informed consent violations, including patients that have had cerebral spinal fluid (CSF) collected but informed consent for CSF not signed

Study specific:

- Visit outside visit intervals specified in protocol:
 - lomustine therapy is held for ≥ 12 weeks from the last dose of lomustine due to any reason and the patient is not discontinued from the study
- If the patient had two prior dose reductions in lomustine therapy and needs a third reduction due to toxicities but is not discontinued from lomustine therapy
- Failure to perform PK collections
 - only collections "not done" are considered significant protocol violations.
- Failure to collect samples of tumor tissue (at screening only)
- Failure to perform safety procedures or missing safety measurements per requirements in Study Schedule (Attachment 1 in Protocol)
 - Hematology/chemistry
 - ECG
 - ECHO

Note: only collections "not done" are considered significant protocol violations.

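### The SAP 6.8 compliance percentage divides by tablets dispensed, which conflicts with the protocol's tablets-expected measure and with the SAP's own rule for early stoppers

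*SAP*

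**What the plan says.** Protocol 12.2.5 sets the measure: "The number of tablets taken relative to the number expected to be taken will be summarized by cycle and treatment arm".

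SAP 6.8 defines a compliant cycle as 10 to 14 dosing days in which at least a redacted percentage "of the allocated LY2157299 prescribed dose has to be administered within each cycle". It makes an exception for patients who stop before reaching 10 dosing days: they count as compliant if the same kind of percentage "of LY2157299 prescribed dose is administered up to the time of discontinuation".

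The same section then says "The level of compliance in percent for a cycle will be calculated as follows". The numerator is 10 times plus 50 times the tablets dispensed minus returned. The denominator is 10 times plus 50 times the tablets dispensed. The same term for tablets is used for both strengths. The result is summarised by cycle and arm, averaged across cycles for an overall figure, and listed per patient next to the tablet counts.

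Two other places set thresholds. SAP 6.15 lists as a violation that "Treatment compliance with LY2157299 is less than" a redacted percentage of what was prescribed or intended for the cycle. Protocol 9.8 says "Compliance of LY2157299 will be determined by the use of at least" a percentage of the same quantity. Neither refers to the SAP 6.8 formula.

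**The concern.** Dispensed minus returned, over dispensed, is the fraction of the supply that was used. It equals the fraction of the prescribed dose taken only when the supply handed out is exactly what the patient was due to take in that cycle. Nothing in either document says that this holds, and nothing explains the change of denominator.

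Early discontinuation is the clearest failure, because it arises even with an exact cycle's supply and sets the formula against a rule in its own section. The stake is modest. The compliance tables would mix adherence with supply practice and with early stopping, and arms that differ in early stopping or dose reduction would appear to differ in adherence.

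**Working it through.** The plan gives no worked compliance figure to reproduce, so the formula is compared directly with the stated definition.

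**Inputs**
- Tablets due in a full cycle (Protocol 9.1): 3 tablets x 2 per day x 14 days = 84 tablets of 50 mg, or 4200 mg. Check: 3 x 50 mg x 2 = 300 mg/day, the stated dose.
- Tablets dispensed (D): not stated. Protocol 9.2.1 describes the packaging without a quantity, so every D below is an assumption.
- Tablets returned (R): all unused tablets are assumed returned and counted.

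**Measures**, with 50-mg tablets only:
- SAP formula: 100 x (D - R) / D
- Definition: 100 x tablets taken / tablets prescribed up to that point

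**1. Full cycle, exact supply.** D = 84, R = 0. Both measures give 100%, so they agree here.

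**2. Every dose taken, early stop, D = 84.**

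| Stops on day | Taken | SAP formula | Definition |
|---|---|---|---|
| 5 | 30 | 30/84 = 35.7% | 30/30 = 100% |
| 7 | 42 | 42/84 = 50.0% | 42/42 = 100% |
| 9 | 54 | 54/84 = 64.3% | 54/54 = 100% |

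All three patients fall under the SAP 6.8 exception and are compliant by its wording. Averaging carries the error forward: one perfect cycle followed by a day-5 stop gives (100 + 35.7)/2 = 67.9%.

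**3. Reduction within a cycle, D = 84.** For arithmetic only, suppose 6 tablets a day for 7 days and then 3 a day for 7 days, all taken as prescribed: 42 + 21 = 63. The formula gives 63/84 = 75.0%; the definition gives 63/63 = 100%.

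**4. Spare tablets, all 84 doses taken.** D = 90, 96, 105 or 112 gives 84/90 = 93.3%, 84/96 = 87.5%, 84/105 = 80.0% or 84/112 = 75.0%. The definition gives 100% each time.

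**5. Errors in the other direction.** With 60 dispensed and none returned, the formula gives 60/60 = 100% against 60/84 = 71.4% of expected. With 96 dispensed and none returned, it gives 96/96 = 100% against 96/84 = 114.3%. The formula cannot exceed 100%.

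**6. Tablet strengths.** Read literally, with one term for both strengths, the weights cancel: [10(D - R) + 50(D - R)] / (10D + 50D) = 60(D - R)/60D = (D - R)/D. Suppose 84 tablets of 50 mg are all taken and 30 of 10 mg are dispensed and all returned. Strength-specific counts give 4200/(4200 + 300) = 93.3%; pooled counts give 84/114 = 73.7%. The text does not settle which is meant, and neither equals the 100% of prescribed dose.

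**The case against.** The strongest reply is that the formula is only descriptive. SAP 6.8 defines being compliant separately and on the prescribed dose, uses the percentage for summary statistics and a listing, and lists the raw counts so that a reader can see what happened. Dose intensity in SAP 6.13.1 uses a planned dose that does not depend on tablets dispensed, and reductions, delays and omissions are reported there with reasons. If each pack holds exactly 84 tablets, the measures agree for every full-dose cycle that runs to day 14. Most of this stands and limits the point, but it does not remove the early-stop conflict, which needs no spare tablets.

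Three stronger readings are tempting, and the documents do not support them.

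- *The formula triggers protocol violations or discontinuation.* SAP 6.15 and Protocol 9.8 word their thresholds on the prescribed or intended amount and do not cite the formula. Discontinuation under Protocol 9.8 follows discussion between the sponsor and the investigator. What remains is a risk: SAP 6.15 identifies some violations by programming, and SAP 6.8 has the only compliance percentage the SAP defines.
- *Patients who take every dose over a full cycle will be classed as noncompliant.* This needs an unstated pack size and a threshold that is redacted almost everywhere. The figure 80 is legible only in Protocol 9.8. If it is the threshold, a full taker fails only above 84/0.80 = 105 tablets, an overage of 25%.
- *The formula hides overdosing.* This percentage cannot show it, but SAP 6.15 lists incorrect dosing, including more than intended, as a violation of its own.

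**Conclusion.** The denominator in SAP 6.8 is wrong as written: it contradicts Protocol 12.2.5 and the prescribed-dose definition, with its early-stop exception, in the same section. With 84 tablets dispensed and unused tablets returned, both assumed, the shortfall for a fully adherent early stopper is 64.3, 50.0 or 35.7 percentage points at day 5, 7 or 9 (100 minus the score). The spare-tablet, under-dispensing and mid-cycle reduction figures show direction and possible size only. How many patients are affected cannot be stated.

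The documented reach is the compliance summaries and the patient listing. The SAP 6.15 violation count is affected only if the formula is reused there. The overall survival analysis is not affected, and no analysis population is defined by this percentage. This is a minor point, worth correcting because the correction is cheap.

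**What to change.** In SAP 6.8:
- Numerator: 10 x (10-mg tablets dispensed minus 10-mg tablets returned) + 50 x (50-mg tablets dispensed minus 50-mg tablets returned), with the strengths labelled.
- Denominator: the mg prescribed over the planned dosing days of that cycle, up to discontinuation and allowing for documented dose changes.
- Allow values above 100%.
- State whether the cut at discontinuation also applies to patients who stop on or after dosing day 10, since the present exception covers only those who stop before completing 10 dosing days.

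In SAP 6.15, state that the violation flag uses this same derived percentage.

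The cost is a short SAP edit and one derivation rule. SAP 6.13.1 has dosing captured on scheduled days only (Days 1, 3, 7, 12 and 14 of Cycle 1; Days 1, 6 and 12 from Cycle 2), so a convention is needed for dose changes between those days. SAP 6.13.1 already requires omissions, adjustments and early discontinuation to be accounted for in cumulative dose, so the same convention can serve both. The change does not cure tablets that are never returned, which inflate any measure based on tablet counts.

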6.9. Concomitant Therapy

All medications will be coded to the generic preferred name according to the current World Health Organization (WHO) drug dictionary. All concomitant medications listings will include both the term reported in CRF and the WHO dictionary term for enrolled patients in each arm and if concomitant medication use is due to adverse event (AE), the associated AE will also be listed.

Enzyme-inducing and non-enzyme inducing anti-epileptic drug treatments will be determined retrospectively and indicated in the listings.

Patients with concomitant steroid use will be listed separately by each arm. Dose information including total daily dose and any dose modification at the start of each cycle will be provided in this listing.

Surgery for palliative reasons and carried out prior to discontinuation from study treatment will be captured separately.

Anti-cancer systemic therapy, radiotherapy and surgery that occurs post discontinuation of study treatment is captured separately from concomitant medication as the existence of such therapies can lead to censoring of time to event endpoints. Patients that received post discontinuation therapies will be listed by treatment arms.

6.10. Efficacy Analyses

The following are definitions of the primary and secondary efficacy endpoints:

Primary Endpoint:

- **Overall Survival (OS) duration** is measured from the date of randomization to the date of death from any cause. For each patient who is not known to have died as of the data-inclusion cut-off date for a particular analysis, OS will be censored for that analysis at the date of last contact prior to the data inclusion cutoff date (contacts considered in the determination of last contact date include AE date, lesion assessment date, visit date, and last known alive date). For OS analysis, death is considered an event.

Secondary Endpoints:

- **Progression-Free Survival (PFS) duration** is measured from the date of study enrollment (randomization) to the date of first observation of objective progression or death from any cause, whichever occurs first. For patients who are not known to have died or progressed as of the data-inclusion cut-off date, PFS time will be censored at the date of the last objective progression-free disease assessment prior to the date of any subsequent systematic anticancer therapy.
- **Progression-Free Survival rate at CCI** is defined as the proportion of patients not having objective progression or death at CCI respectively after the time from date of study enrollment (randomization) estimated from the PFS distribution.
- **Survival rate at 12 months** is defined as the proportion of patients alive 12 months after start of treatment, even if they have progressed, estimated from the overall survival distribution.
- **Overall Response Rate (ORR)** is defined as the proportion of patients who achieved a best overall response of either complete response (CR) or partial response (PR). The overall response rate for each treatment group will be estimated by dividing the total number of confirmed responders by the number of patients who received at least 1 dose of study treatment. Response will be evaluated based on the Response Assessment in Neuro-Oncology (RANO).
- **Disease Control Rate** is defined as the proportion of patients who achieved a best response of CR, PR or stable disease (SD) per RANO criteria. This rate will be estimated for each treatment group by dividing the total number of patients that had CR, PR or SD by the number of patients who received at least 1 dose of study treatment. Best response of SD is defined as disease that does not meet the criteria for CR, PR, or progressive disease (PD) and has been evaluated at least one time, and at least 6 weeks after baseline assessment. Patients without a valid response assessment at least 6 weeks after baseline assessment are assigned a best response of nonevaluable unless progression has already occurred.

All primary and secondary efficacy endpoints will be analyzed for patients who received at least one dose of study treatment. All time-to-event endpoints will be analyzed using the Kaplan-Meier method. Covariates may also be included in these time-to-event models to account for variation in survival time. A Bayesian model will be used to estimate the hazard ratio of overall survival between the treatment arms.

Table JBAL.6.10. An Overview of the Efficacy Analyses

Efficacy Endpoint	Statistical Analysis	SAS Procedures
Primary analysis:		
Overall survival	A Bayesian OS model to estimate the hazard rates and ratios (HR) of OS and 90% predictive interval between LY2157299 plus lomustine therapy and lomustine plus placebo therapy	Non SAS - FACTS
Secondary analyses:		
Overall survival	
The same Bayesian OS model in the primary analysis is used in secondary analysis to estimate the HR between LY2157299 monotherapy and lomustine plus placebo therapy, and between LY2157299 plus lomustine therapy and LY2157299 monotherapy
 
Kaplan-Meier method will be used to estimate median survival time, OS rate at 12 months, and its 95% confidence interval for the treatment arms
 
Proportional hazard model will be used to estimate the hazard ratio of survival and 95% confidence interval between treatment arms, control for other factors
	Non SAS - FACTS
Progression-free survival	
Kaplan-Meier method will be used to estimate median PFS, PFS rates at CCI, and its 95% confidence interval for the treatment arms
 
Proportional hazard model will be used to estimate the hazard rate and ratio of PFS and 95% confidence interval of the 3 treatment arms and between the treatment arms
	LIFETEST
Overall response rate (CR or PR) Disease control rate (CR, PR or SD)	
The overall response rate will be estimated from dividing the total number of responders ([CR or PR]) by the number of patients that have at least 1 dose of study drug in each treatment arm
 
The disease control rate will be estimated from dividing the total number of patients with CR, PR or SD by the number of patients that have received at least 1 dose of study drug in each treatment arm
 
The exact 95% confidence interval for ORR and disease control rate will also be provided for each arm
	PHREG
		REQ

